15.2. Annex II: Initial Screening Form

Participant ID:

Date of screening:

Personal Information:

- Name:
- Date of birth:
- Age:
- Gender:
- Ethnicity:
- Address:
- City:
- State:
- Zip code:
- Phone number:
- Email address:

Medical Information:

- Diagnosis of cerebral palsy: Yes or No
- GMFCS level: III or IV
- Other medical conditions that may impact their ability to participate in the study (e.g., uncontrolled seizures, cardiac conditions, respiratory conditions):
- Current medications:
- History of surgery related to cerebral palsy:
- History of seizures:
- Allergies:
- Medical devices or equipment currently used:
- Cognitive or communication impairments that may impact their ability to follow instruction:

Social and Demographic Information:

- Parent/guardian name:
- Relationship to participant:
- Occupation:
- Education level:
- Family socio-economic status:
- Primary language spoken at home:
- Other languages spoken:
- Access to transportation:

Physiotherapy History

- Where does he/she do physiotherapy?
- How often?
- How is it? What does he/she do?
- What's the duration of each session?
- How's the adherence? Does he/she cry or laugh during the session?
- Do you get recommendations?

Other

- Is the participant able to attend physiotherapy sessions twice a week for 16 weeks? Yes or No
- Has the participant been involved in any other clinical research studies in the past 3 months? Yes or No
- Any other relevant information:

15.3. Annex III: Play Therapy Activities and Games

Photo of the Activity	Description
	
With this activity, we aim to encourage our child to keep his or her head upright, thus improving his or her head control, while also offering them an entertaining game.

	
With this activity, we aim to encourage our child to maintain trunk control while attempting to score a ball into a hoop on the ground.

	
In this activity, we encourage the child's standing with support at a table or shelf where there is a toy that motivates him or her to stand up (with or without help).

	
In this activity, we promote the child's sitting position with greater or lesser support surface, while also encouraging dorsal stretching by attempting to reach a motivating toy.

	
In this activity, we encourage the extension of the back while trying to play. Also, we gain back strength as our child needs to keep the attention in height.

	
In this activity, we encourage the pelvis stability on knees position and to keep the back straight we play with the child in his shoulders' plane.

	
In this activity we encourage our child to gain standing stability while playing with a toy that motivates him or her to stand up (with or without help), which is in a table or shelf.

	
In this activity, we encourage the child's sitting position with greater or lesser support surface, while promoting rotation as he or she needs to pass objects from one side to the other.

	
In this activity, we can construct an obstacle course out of cones, beanbags, hula hoops, and other things that will test the child's mobility. It's useful to strengthen gross motor function and to encourage the kid to crawl, roll, or walk around the obstacles. They can use their devices or orthoses if necessary.

Other play therapy activities

- **Sensory Play:** We can use sensory play to activate the senses and encourage mobility in your child. Finger painting, sand play, water play, and playdough are some examples.

- **Animal Walks:** We can make the child imitate various animal motions, such as cat crawls, crab walks, and bunny hops. This aids in the improvement of balance, coordination and muscle strength.
- **Balloon Games:** We can use balloons to play activities that improve hand-eye coordination, spatial awareness, and upper body strength. For example, we can play balloon volleyball, where the child needs to maintain the balloon in the air and pass it to the physiotherapist.
- **Ball Games:** We can use a soft ball or beach ball to play catch or soccer. This can aid in the development of hand-eye coordination, upper-body strength, and gross motor abilities.
- **Musical chairs:** We can play the game of musical chairs, encouraging him or her to walk or crawl around the chairs and sit down when the music stops. This can aid in the improvement of mobility, balance, and coordination.
- **Simon Says:** We can play Simon Says with the child, giving him or her directions like "Simon says touch your toes" or "Simon says crawl under the bridge." This game can help to improve the listening abilities, the ability to follow directions, and the general motor coordination.

We may remember that these are just some proposals and that each activity should be adapted to the patient needs and interests.

15.4. Annex IV: Logbook

Patient nº						
Data						
Session nº						
Assistance	 Yes					0p
	 No					1p
Time of session done	 0-15 minutes					1p
	 15-30 minutes					2p
	 30-45 minutes					3p
Exercises	1	2	3	4		
Task completion	 Not done	 Not done	 Not done	 Not done	0p	
	 Initiates	 Initiates	 Initiates	 Initiates	1p	
	 Partially complete	 Partially complete	 Partially complete	 Partially complete	2p	
	 Completes	 Completes	 Completes	 Completes	3p	
Did you help him/her?	 Yes	 Yes	 Yes	 Yes	1p	
	 No	 No	 No	 No	0p	
Did he/she laugh?	 Yes	 Yes	 Yes	 Yes	1p	
	 No	 No	 No	 No	0p	
Did he/she cry?	 Yes	 Yes	 Yes	 Yes	0p	
	 No	 No	 No	 No	1p	
Did he/she get mad?	 Yes	 Yes	 Yes	 Yes	0p	
	 No	 No	 No	 No	1p	
Did the parents follow the recommendations?	 Yes				1p	
	 No				0p	
TOTAL SCORE					  / 12	

This is the logbook that will be used during the treatment adherence measurement, but the physiotherapist will not have the punctuation in order to not bias him or her.

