9.3. Intervention

The intervention will consist of two groups: a play therapy-based physiotherapy group (experimental group) and a conventional physiotherapy group (control group).

The play therapy-based physiotherapy group will receive 45 minutes sessions of play therapy-based physiotherapy twice a week for 16 weeks (32 sessions in total). The play therapy-based physiotherapy sessions will be conducted by a trained and licensed physiotherapist and will be planned incorporating playing activities such as ball games, obstacle courses, music, sensory toys, and pretend play combined with standard physiotherapy exercises ([Annex III](#)). All that, based on the child's interests and abilities, with the aim of engaging the child in a pleasant and enjoyable activity that simultaneously enhances gross motor function. Moreover, the physiotherapist will offer feedback and positive reinforcement throughout play therapy sessions to encourage adherence. The therapist will also give advice and assistance to the child as needed to ensure that they can do each exercise safely and efficiently and the family will receive home recommendations based on play to assist their worries and questions.

The conventional physiotherapy group will receive 45 minutes sessions of conventional physiotherapy twice a week for 16 weeks (32 sessions in total). The conventional physiotherapy sessions will also be conducted by a trained and licensed physiotherapist and will include standard physiotherapy exercises following the international clinical practice guideline from 2022 of Jackman M, et al (3). These sessions will be planned for each child's needs and goals, for improving gross motor function and increasing treatment adherence. Moreover, the physiotherapist will offer feedback and positive reinforcement throughout sessions to encourage adherence. The therapist will also give assistance as needed to ensure that they can do each exercise safely and efficiently and the family will receive home recommendations based on their worries and questions.

Both groups will get their respective treatments at the same location, and the study team will rigorously monitor adherence to the intervention program. The study team will also gather information on any adverse events or problems that may occur throughout the intervention.

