9.4.1. Treatment Adherence

Treatment adherence will be measured as a primary outcome and refers to the extent to which a patient follows or complies with the recommended or prescribed treatment plan and it's a process in which the appropriate treatment is decided after a proper discussion with the patient and its family to establish its goals and motivations (B). Having into account this definition, treatment adherence will be measured using objective and subjective measures noted in a logbook by the physiotherapist after each session ([Annex IV](#)). In this logbook it will be measured the percentage of completed physiotherapy sessions out of the total number of sessions scheduled, the percentage of exercises done in each session, how the child felt while doing each exercise and if parents/carers have followed the recommendations given. The maximum punctuation is 12 and the minimum is 1 point. The physiotherapist will not know which punctuation receive each option in order to reduce the risk of bias.

In addition, the Goal Attainment Scale (GAS) will be used as a method to measure if the goals determined before starting the intervention has been achieved or not (B), which is highly related to treatment adherence. This goal setting will be done based on parents or guardians and children's needs and motivations, which will be commented with the physiotherapist so that he or she can plan a tailored physiotherapy program. Moreover, all the goals will follow the SMART criteria to try to be as much objective and measurable as possible.

B. Cusick A, et al. A comparison of goal attainment scaling and the Canadian Occupational Performance Measure for paediatric rehabilitation research. *Pediatr Rehabil.* 2006 Jun;9(2):149-57.

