9.5. Data Collection

Many steps will be applied during the study to guarantee the security and confidentiality of participants' data. To begin, all data obtained will be kept totally secret and only authorized members of the study team will have access to it. To do the allocation concealment, a statistician will generate the randomization list by given to participants a unique identification number, which will be used to assign them to one or another group.

For the outcome measure assessment different procedures will be conducted. The GAS, the GMFM-88 and the CP QoL-Child will be done at baseline, after 5, 10 and 16 weeks and at the follow-up assessment at 24 weeks. In the baseline the GAS will be used as a way for the physiotherapist to plan the intervention and in the mid-term assessments the goals achievement will be measured, all this by the physiotherapist. The GMFM-88 will be assessed by the outcome assessor and the CP QoL-Child will be done by parents or caregivers who will give the questionnaire to the research assistants for them to score it and save it.

On the other hand, the logbook will be completed by the physiotherapist after each participant session and at the end of the 16 weeks intervention will be given to the research assistants to do the data collection and after that, the analysis.

All paper-based data will be stored in locked cabinets in a secure research facility and electronic data will be kept on a password-protected computer and will be stored and managed from Microsoft One Drive cloud, which contains a double security system. Exclusively authorized people will be able to access to the data.

Only de-identified data will be shared in any publications or presentations emerging from the study to protect the privacy and confidentiality of participants. Without express written authorization, participants' personal data will not be shared with anybody outside of the study team.

Once all the study is finished, the obtained data may be maintained for a limited time, as needed by institutional guidelines, before being securely deleted to prevent unauthorized access or use. Overall, the research team is committed to maintaining the greatest levels of privacy and confidentiality to protect the safety and well-being of all study participants.

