Physiotherapists (PTs)	
 • They will be trained on the study protocol and will follow it rigorously • Deliver physiotherapy interventions • Monitor participant progress and adjust interventions as needed • Give parents recommendations • Assess treatment adherence logbook and GAS • Document intervention delivery

Table 2: Roles and responsibilities of research team members.

		Month 0				Month 1				Month 2				Month 3				Month 4				Month 5							
		1	2	3	4	1	2	3	4	1	2	3	4	1	2	3	4	1	2	3	4	1	2	3	4	1	2	3	4
Tasks	Responsible	PHASE I: PLANNING AND PREPARATION OF THE PROJECT																											
Research Question + Hypothesis + Objectives	PR																												
Literature Review + Write Background	PR																												
Study Design + Creation of the protocol	PR																												
Ethics Approval	PR																												
Find Funding Sources	PR																												
Recruitment of the Research Team	PR																												

		Month 4				Month 5				Month 6				Month 7				Month 8				Month 9				Month 10				Month 11				Month 12				Month 13			
		1	2	3	4	1	2	3	4	1	2	3	4	1	2	3	4	1	2	3	4	1	2	3	4	1	2	3	4	1	2	3	4	1	2	3	4	1	2	3	4
Tasks	Responsible	PHASE II: PARTICIPANT RECRUITMENT, INTERVENTION AND ASSESMENT																																							
Recruitment + Screening + IC	RAs + PR																																								
Randomization	PR + ST																																								
Baseline Assesment (week 0)	OAs + RAs																																								
Mid-term Assesment I (week 5)	OAs + RAs																																								
Mid-term Assesment II (week 10)	OAs + RAs																																								
End-Intervention Assesment (week 16)	OAs + RAs																																								
Follow-up Assesment (week 24)	OAs + RAs																																								
Treatment Adherence Assesment	PTs + RAs																																								
Intervention (16 weeks)	PTs																																								

		Month 13				Month 14				Month 15				Month 16			
		1	2	3	4	1	2	3	4	1	2	3	4	1	2	3	4
Tasks	Responsible	PHASE III: DATA ANALYSIS AND REPORT															
Data cleaning + Analysis	PR + ST																
Interpretation of Results	PR + RAs																
Final Report	PR																
	PR + RAs	PHASE IV: DISSEMINATION OF RESULTS															

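### The logbook's parent row has no box for 'no recommendation in force', so having nothing to follow scores as non-adherence; an arm bias is possible but not established

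*Protocol*

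**What the plan says.** Treatment adherence is a primary outcome (Protocol 9.4, 9.4.1). One component of its logbook is "if parents/carers have followed the recommendations given". In Annex IV this becomes one row, "Did the parents follow the recommendations", with Yes = 1p and No = 0p. There is no third box, and no field records whether a recommendation had been given.

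Section 9.5 says that "the logbook will be completed by the physiotherapist after each participant session", and section 9.3 schedules 32 sessions per child in each arm. Section 9.4.1 gives the score range: "The maximum punctuation is 12 and the minimum is 1 point".

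Section 9.3 describes the home advice arm by arm:
- Play arm: "the family will receive home recommendations based on play to assist their worries and questions".
- Conventional arm: "the family will receive home recommendations based on their worries and questions".

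Table 2 (section 11) lists "Give parents recommendations" among the physiotherapists' tasks without splitting it by arm. The protocol does not say how often recommendations are given. Section 9.6 adds that each part of the logbook will be analysed in the search for predictors of adherence, by regression with treatment group among the covariates.

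**The concern.** Section 9.4.1 presupposes that a recommendation was given; the form does not check it. When none is in force, the therapist must tick No or leave the row blank, and either adds 0 to the total. The row then mixes two things: what the therapist provided and what the family did with it. Only the second is adherence.

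This is a fault of data capture. Once the sessions have been logged, no analysis rule can separate 'none given' from 'not followed'. The therapist who gives the advice also ticks the box and, by section 9.1, knows the arm. Hiding the point values from the therapist does not help, because the missing answer is the problem.

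At stake is a primary outcome in which a difference in how often advice is given would appear as a difference in adherence, with family behaviour identical.

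**Working it through.** **1. The plan's own range.** Taking the Annex IV points as printed and counting each exercise row once:
- Minimum: attendance 0 + time 1 + task 0 + help 0 + laugh 0 + cry 0 + mad 0 + parents 0 = 1.
- Maximum: 1 + 3 + 3 + 1 + 1 + 1 + 1 + 1 = 12.

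This reproduces the stated 1 and 12. The parent row is 1/12 = 8.3% of the maximum. (Summing all four exercise columns would give 1 + 3 + 4 × 7 + 1 = 33, so the stated 12 implies one value per exercise row.)

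**2. Session 1.** No trial recommendation has yet been given, so the row cannot properly be answered Yes. The loss is at most 1 point in one of 32 sessions: 1/32 = 0.03 points of the child's mean. It is the same in both arms and cancels in the comparison.

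**3. Later sessions.** Let f be the chance that a recommendation in force is followed, equal in both arms, and g the difference between arms in the share of sessions with one in force. The spurious difference in mean session score is g × f. The protocol gives neither value. Assuming f = 0.8:

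| g | g × f (points of 12) |
|---|---|
| 0 | 0 |
| 0.10 | 0.08 |
| 0.20 | 0.16 |
| 0.40 | 0.32 |

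The ceiling, g = f = 1, is 1 point. The sign depends on which arm gets advice more often.

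**4. Effect on a test of the total score.** With 32 per arm (section 9.2.1), a two-sided t-test at 0.05 and no true difference, the standard error is SD × √(2/32) = 0.25 × SD. The SD of a child's mean score is not given, so 1.0, 1.5 and 2.43 are assumed. (2.43 is the Annex I figure, whose outcome variable is not named.)

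| Spurious difference | SD 1.0 | SD 1.5 | SD 2.43 |
|---|---|---|---|
| 0 | 0.05 | 0.05 | 0.05 |
| 0.08 | 0.06 | 0.06 | 0.05 |
| 0.16 | 0.10 | 0.07 | 0.06 |
| 0.32 | 0.24 | 0.13 | 0.08 |

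The entries are chances of a significant result.

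**5. The row analysed alone.** On its own 0 to 1 scale the same g × f is 0, 8, 16 or 32 percentage points. With an assumed SD of 0.3 or 0.4 for a child's proportion of Yes, the standard error is 0.075 or 0.10. The chance of a falsely significant arm difference, again from a two-group t-test, is:

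| Spurious difference | SD 0.3 | SD 0.4 |
|---|---|---|
| 0 | 0.05 | 0.05 |
| 0.08 | 0.18 | 0.12 |
| 0.16 | 0.56 | 0.35 |
| 0.32 | 0.99 | 0.88 |

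**The case against.** A reader might infer from section 9.3 that conventional-arm families get advice only when they raise a worry, while play-arm families get it regardless, so that the form favours the play arm. The text does not support this. Both sentences say that the family will receive home recommendations, and both refer to worries and questions. The stated difference is in content, play-based or not. Table 2 makes giving recommendations a duty towards all families, and no section says that either arm may receive none. With equal frequency the artefact is zero. This part of the objection stands: a bias between arms, and its direction, cannot be claimed.

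Two further points stand in part. Advice may remain in force from one session to the next, so sessions with nothing to follow may be few after the first. Section 9.7 also promises an explanation of how to complete the logbook, which could address the case. But instructions cannot supply an answer that the form does not offer, and a blank adds the same 0 as No in a plain sum.

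The row is also only 1 of 12 points. That limits the harm to the total, but not to the separate analysis of the row.

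**Conclusion.** The form has a small but real defect: it cannot distinguish nothing to follow from advice not followed, and it scores both as 0 in a primary outcome. What is certain is session 1, which costs at most 0.03 points of a child's mean score equally in both arms and biases nothing between them.

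Bias between arms requires a gap in how often advice is in force, which the protocol neither states nor excludes. Over an assumed gap of 0 to 40 percentage points with 80% following, the spurious difference is 0 to 0.32 of 12 points per session, in either direction. For the total score this is modest over most of that range. For the row alone it could be misleading if the gap is large. All of these sizes rest on assumed values of f, g and the SDs. The point is a cheap improvement, not a threat to the trial, but it must be made before data collection because the missing information cannot be recovered later.

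**What to change.** - Add a third box to the parent row of Annex IV: 'no recommendation in force'.
- For such sessions leave the row out of both the points and the maximum: score out of 11 and multiply by 12/11.
- Analyse the row on its own as the proportion of Yes among sessions with a recommendation in force.
- Report by arm the number of sessions with a recommendation in force. Any gap in provision is then visible.

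Stating one frequency of home recommendations for both arms would also help, if that is what is intended.

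For the row alone this removes the artefact under the assumptions above. For the total, rescaling in effect fills the row with the child's average on the other rows, s/11, so a remainder of g × (f − s/11) is left. With g = 0.40, f = 0.8 and an assumed s/11 of 0.6, that is 0.40 × 0.2 = 0.08 points instead of 0.32; at s/11 = 0.8 it is 0.

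The cost is one more box, a slightly more complex total, a denominator for this row that varies between children, and a few sentences of scoring rule.

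### The attendance row of the adherence logbook is keyed backwards: attending earns 0 points and absence earns 1, so no attended session can reach the stated maximum of 12

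*Protocol*

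**What the plan says.** Section 9.4.1 gives adherence its status: "Treatment adherence will be measured as a primary outcome". It defines adherence as "the extent to which a patient follows or complies with the recommended or prescribed treatment plan", so a higher score should mean more adherence. On attendance it says: "In this logbook it will be measured the percentage of completed physiotherapy sessions out of the total number of sessions scheduled". It gives the score range as: "The maximum punctuation is 12 and the minimum is 1 point".

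Annex IV holds the form and its point key, and states its purpose: "This is the logbook that will be used during the treatment adherence measurement". The first scored row reads "Assistance Yes 0p", with 1 point for No. Session time follows, from 1 point for the shortest band up to "30-45 minutes 3p". Task completion scores 0 to 3. Help, laughing, crying, anger and parents following the recommendations score 0 or 1 each. The total is out of 12.

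The physiotherapist fills in the form after each session and does not see the points (section 9.4.1, Annex IV). Section 9.6 plans to analyse each part of the logbook by regression, and both 9.6 and Annex V list the attendance rate as a separate variable.

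**The concern.** *Assistance* can only sensibly mean attendance here. The Spanish Resumen uses *asistencia* where the English abstract has *attendance*. Section 9.4.1 requires the logbook to record completed sessions, and no other row asks whether the child came. Help from the therapist has its own row, "Did you help him/her", which is keyed the other way round (Yes = 1, No = 0).

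On that reading the row runs against the protocol's own definition of adherence. More session time, more of the task completed and parents following the advice all earn more points, while turning up earns none and staying away earns one. At stake are the logbook total and, in the part-by-part regressions, the sign of the coefficients for this row. The person completing the form cannot notice the slip, because the points are not on that copy.

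**Working it through.** **Inputs.** Point values from Annex IV; stated range 1 to 12 from section 9.4.1; 32 scheduled sessions per child from section 9.3. Attendance proportions and mean attended scores are not in the protocol and are assumed below.

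**1. Reproduce the stated range.** Order of terms: attendance, time, task, help, laugh, no crying, no anger, parents.
- Maximum: 1+3+3+1+1+1+1+1 = 12.
- Minimum: 0+1+0+0+0+0+0+0 = 1.

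This matches 9.4.1 if the four exercise columns are counted once (one exercise, or their mean). Summing all four gives a maximum of 1+3+4×(3+1+1+1+1)+1 = 33, which does not match.

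**2. Split the range by attendance.**

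| Session | Printed key | Row reversed |
|---|---|---|
| Attended, lowest | 0+1 = 1 | 1+1 = 2 |
| Attended, highest | 0+3+3+1+1+1+1+1 = 11 | 1+3+3+1+1+1+1+1 = 12 |
| Missed, all other rows 0 | 1 | 0 |

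Under the printed key, 12 requires a child marked absent who is also credited with 30-45 minutes and completed exercises, which cannot happen. A missed session with the other rows at 0 ties with the lowest attended session. The formal range is 1 to 12 under either key, so the range alone does not reveal the error; the impossible route to 12 does.

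**3. The row alone, if sheets are completed for missed sessions.** Mean row score per scheduled session is 1-p as printed and p when reversed, where p is the attendance proportion.
- 90% versus 70%: printed 0.10-0.30 = -0.20; reversed 0.90-0.70 = +0.20; change 0.40.
- 90% versus 80%: printed 0.10-0.20 = -0.10; reversed 0.90-0.80 = +0.10; change 0.20.
- Summed over 32 sessions, a child who misses 8 gets 8 points as printed and 24 when reversed; a child who attends all 32 gets 0 and 32.

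**4. The total, if sheets are completed for missed sessions.** Let A be the mean attended score under the printed key, taken as equal in both arms, with missed sessions scoring 0 on all other rows. The mean per scheduled session is pA + (1-p)×1 as printed and p(A+1) when corrected. The between-arm differences are (p1-p2)(A-1) and (p1-p2)(A+1). At 90% versus 70%:
- A = 8: 0.2×7 = 1.4 printed; 0.2×9 = 1.8 corrected.
- A = 4: 0.2×3 = 0.6 printed; 0.2×5 = 1.0 corrected.

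The loss is 0.40 in each case. The printed total still favours the arm that attends more for every A above 1.

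If *No* were ticked literally for crying and anger at a missed session, that session would score 1+1+1 = 3 as printed and 2 when corrected. The differences become 0.2×(A-3) and 0.2×(A-1). The loss is again 0.40, with reversal only if A is below 3.

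**5. No sheet for missed sessions.** Every sheet is then ticked Yes, the row is 0 throughout, and it adds nothing to the between-arm difference. The highest possible score is 11.

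**The case against.** The best defence concerns the effect, not the key. Sections 9.4.1 and 9.5 have the logbook completed after each session. If that means only sessions that took place, the row is constant and biases nothing. This stands as a possibility: the *No* box suggests sheets for absences, but the protocol does not settle it and states no rule for combining sessions.

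A reader might infer that the key turns the whole adherence score round, so that the arm attending less would win. The document does not support that. The time, task and other rows still reward attended sessions, and the working shows attenuation in all but extreme cases. A reader might also infer that the attendance data are spoiled. They are not: the attendance rate comes from the ticks, and the raw forms can be rescored.

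Three smaller points:
- The 11 counts the point for being helped, and the protocol does not say whether help reflects better adherence. A child who does everything unaided scores 10 (0+3+3+0+1+1+1+1), further from 12, so the conclusion holds.
- *Assistance* could be read as help, a sense section 9.3 does use. That would duplicate the help row with opposite scoring and leave the logbook without the attendance item that 9.4.1 requires.
- A transposition in converting the table to text cannot be wholly excluded. But each label stands on the same line as its points, and the other rows read in a consistent order.

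**Conclusion.** The attendance row is wrong as printed. That conclusion needs only the Annex IV key, the meaning of *Assistance*, and the exercise rows counted once, which is the count that reproduces the stated range.

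The size depends on a rule the protocol does not give. With sheets for missed sessions, the between-arm difference in the total is understated by twice the difference in attendance proportion: 0.40 points per session at an assumed 90% versus 70%, and 0.20 at 90% versus 80%, on a 12-point scale. This is attenuation, not normally reversal. In a regression on this row alone the sign is wrong. Without such sheets there is no between-arm bias, but the row carries no information and the stated maximum cannot be reached. In either case an item of a primary outcome contradicts its definition and should be corrected before anything is scored.

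**What to change.** In Annex IV, set *Assistance* to Yes = 1 point and No = 0 points.

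Reversing the row alone is not enough, because the stated minimum of 1 would then fit neither an attended session (2 to 12) nor a missed one (0). In section 9.4.1, state that:
- a sheet is completed for every scheduled session, attended or not;
- a missed session scores 0, with no points from the other rows;
- attended sessions range from 2 to 12, so the overall minimum is 0 in place of 1.

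The cost is one row of the key and a few sentences. The form as ticked does not change, and the physiotherapists' copy carries no points, so scores can be computed under the corrected key without loss. The one operational addition is a sheet for each missed session, if that is not already intended.
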